#### 8.1.7 Storage and Stability

Store vials in the original carton under refrigeration at 2° to 8°C (36° to 46°F) until time of use. Protect from direct sunlight. DO NOT FREEZE. Since panitumumab does not contain preservatives, any unused portion remaining in the vial must be discarded.

The diluted infusion solution of panitumumab should be used within 6 hours of preparation if stored at room temperature, or within 24 hours of dilution if stored at 2° to 8°C (36° to 46°F). DO NOT FREEZE.

Temperature excursions outside of the specified ranges for a duration of over 15 minutes need to be reported to the PI and Amgen; such agent should not be used without written approval from Amgen.

#### 8.1.8 Handling

Qualified personnel, familiar with procedures that minimize undue exposure to themselves and the environment, should undertake the preparation, handling, and safe disposal of the agent.

#### 8.1.9 Preparation

The panitumumab dose will be calculated based on the participant's actual body weight at baseline and re-calculated at subsequent doses per institutional guidelines. At a minimum, the dose will be re-calculated if the actual body weight changed by at least  $\pm 10\%$  from the last time the dose was calculated.

Inspect the panitumumab prior to removal from the vial. The solution should be colorless and may contain a small amount of visible translucent-to-white particulates. Do not administer if discoloration is observed.

Panitumumab is to be diluted to a recommended total volume of 100 mL in pyrogen-free 0.9% sodium chloride solution USP/PhEur (normal saline solution, supplied by the site), except for doses higher than 1000 mg which should be diluted to 150 mL in 0.9% sodium chloride solution, USP/PhEur (normal saline solution, supplied by the site). The maximum concentration of the diluted solution to be infused should not exceed 10 mg/mL. The volume of normal saline should be increased as needed to ensure that the maximum concentration of the diluted solution does not exceed 10 mg/mL.

Mix diluted solution by gentle inversion. Do not shake. Discard any unused portion remaining in the vial.

The diluted infusion solution of panitumumab should be used within 6 hours of preparation if stored at room temperature, or within 24 hours of dilution if stored at 2° to 8°C (36° to 46°F). DO NOT FREEZE.

### 8.1.10 Administration

Panitumumab will be administered IV by an infusion pump through a peripheral line or indwelling catheter using a **non-pyrogenic, low protein binding filter with a 0.2 or 0.22-micron in-line filter** infusion set up.

For the 100ml volume, administer the infusion over 60 ( $\pm$  15) minutes by a trained healthcare professional. If the first infusion is well tolerated (ie without any serious infusion-related reactions) all subsequent infusions may be administered over 30  $\pm$  10 minutes.

It is recommended that doses higher than 1000 mg should be diluted to 150 mL in 0.9% sodium chloride solution, USP/PhEur (normal saline solution, supplied by the site) and infused over 90  $\pm$  15 minutes.

Strict adherence to aseptic technique should be used during panitumumab preparation and administration. The bag should be labeled per site pharmacy Standard Operating Procedures and promptly forwarded to the clinical research center for infusion.

A physician or medical staff involved in study evaluation must be available during the administration of panitumumab to assess and treat adverse events that may arise during dosing.

### 8.1.11 Supplier

Panitumumab is FDA approved for the treatment of KRAS (exon-2 codons 12 and 13) WT metastatic colorectal cancer in the first line treatment in combination with FOLFOX or as single agent following progression after fluoropyrimidine, oxaliplatin, and irinotecan containing regimens. The commercially labeled agent will be supplied free of charge from Amgen.

### 8.1.12 Accountability

The investigator, or a responsible party designated by the investigator, must maintain a careful record of the inventory and disposition of the agent (investigational or free of charge) using the NCI Drug Accountability Record or another comparable drug accountability form. (See the CTEP website at <http://ctep.cancer.gov/protocolDevelopment> for the "Policy and Guidelines for Accountability and Storage of Investigational Agents" or to obtain a copy of the drug accountability form.)

### 8.1.13 Destruction and Return

At the end of the study, unused supplies of Panitumumab should be destroyed according to institutional policies. Destruction will be documented in the Drug Accountability Record.

## 8.2 Irinotecan

Irinotecan (CAMPOSTAR) is an FDA approved chemotherapy agent. Please refer to the Package Insert for additional details not provided in this section:

[http://www.sagentpharma.com/Products/Irinotecan/Catalog/Irinotecan\\_PI.pdf?PHPSESSID=e089d1b1c1dd5c6cbe2ce3165369bfd8](http://www.sagentpharma.com/Products/Irinotecan/Catalog/Irinotecan_PI.pdf?PHPSESSID=e089d1b1c1dd5c6cbe2ce3165369bfd8)

### 8.2.1 Other names:

CPT-11, Camptosar

### 8.2.2 Chemical name and molecular formula and molecular weight

Irinotecan hydrochloride trihydrate: (4S)-4, 11-diethyl-4-hydroxy-9-((4-piperidinopiperidino) carbonyloxy)-1H-pyrido[3',4':6,7]indolizino[1,2-b]quino line-3, 14(4H,12H)dione hydrochloride trihydrate. C33H38N4O6•HCl•3H2O. M.W. 677.19

### 8.2.3 Mechanism of action

Irinotecan is a topoisomerase I inhibitor.

### 8.2.4 Human Toxicity

See section 6.1.2.

### 8.2.5 Formulation

Irinotecan is supplied in three forms: 2 mL vials containing 40 mg of drug, 5 mL vials containing 100 mg of drug, and 15 mL vials containing 300 mg of drug. The drug is supplied in brown vials and appears as a pale-yellow-to-yellow crystalline powder and pale yellow transparent solution when reconstituted.

### 8.2.6 Storage and Stability

Irinotecan vials must be stored in a cool, dry place, protected from light. It is stable to the expiration date on its label. Irinotecan is stable for at least 24 hours in glass bottles or plastic bags after reconstitution with D5W.

### 8.2.7 Handling

Qualified personnel, familiar with procedures that minimize undue exposure to themselves and the environment, should undertake the preparation, handling, and safe disposal of the chemotherapeutic agent.

### 8.2.8 Administration

Irinotecan will be diluted with D5W to a total volume of 500 ml and infused intravenously over 90 minutes. Nothing else should be added to the bag.

### 8.2.9 Supplier

Irinotecan is commercially available.

## 8.3 **Leucovorin**

Please refer to the Package Insert for additional details for leucovorin not provided in this section:

[http://dailymed.nlm.nih.gov/dailymed/lookup.cfm?setid=bffe8bc8-  
ea2d-4512-b41d-5a2aa30fd11c](http://dailymed.nlm.nih.gov/dailymed/lookup.cfm?setid=bffe8bc8-
ea2d-4512-b41d-5a2aa30fd11c)

### 8.3.1 Other Names:

Leucovorin Calcium, Wellcovorin, citrovorum factor, folinic acid, 5-formyl tetrahydrofolate, LV, LCV.

### 8.3.1 Chemical name and molecular formula and molecular weight

5-formyl-5,6,7,8-tetrahydrofolic acid: calcium *N*-[4-[[[(2-amino-5-formyl-1,4,5,6,7,8-hexahydro-4-oxo-6-pteridiny)-methyl]amino]benzoyl]-*L*-glutamic acid. C20H21CaN7O7. M.W. 511.51

### 8.3.2 Mechanism of Action:

Leucovorin acts as a biochemical cofactor for 1-carbon transfer reactions in the synthesis of purines and pyrimidines. Leucovorin does not require the enzyme dihydrofolate reductase (DHFR) for conversion to tetrahydrofolic acid. The effects of methotrexate and other DHFR-antagonists are inhibited by leucovorin. Leucovorin can potentiate the cytotoxic effects of fluorinated pyrimidines (i.e., fluorouracil and floxuridine). After 5-FU is activated within the cell, it is accompanied by a folate cofactor, and inhibits the enzyme thymidylate synthetase, thus inhibiting pyrimidine synthesis. Leucovorin increases the folate pool, thereby increasing the binding of folate cofactor and active 5-FU with thymidylate synthetase.

### 8.3.3 Human Toxicity

See section 6.1.3.

### 8.3.4 Supplier

Leucovorin is commercially available.

## 8.4 **5-fluorouracil (5-FU)**

For complete prescribing information, please refer to the FDA approved package insert.

<http://dailymed.nlm.nih.gov/dailymed/archives/fdaDrugInfo.cfm?archiveid=13302>

### 8.4.1 Other Names:

5-Fluorouracil, 5-FU, Adrucil, Efudex.

### 8.4.2 Chemical name and molecular formula and molecular weight

5-fluoro-2,4 (1H,3H)-pyrimidinedione. C4H3FN2O2 MW 130.08

### 8.4.3 Mechanism of Action

Fluorouracil is a pyrimidine antagonist that interferes with nucleic acid biosynthesis. The deoxyribonucleotide of the drug inhibits thymidylate synthetase, thus inhibiting the formation of thymidylic acid from deoxyuridylic acid, thus interfering in the synthesis of DNA. It also interferes with RNA synthesis.

### 8.4.4 Storage and Stability:

Stable for prolonged periods of time at room temperature if protected from light. Inspect for precipitate; if apparent, agitate vial vigorously or gently heat to not greater than 140°F in a water bath. Do not allow to freeze.

## 9.0 **CORRELATIVE/SPECIAL STUDIES**

---

All participants will undergo serial blood sampling for future possible exploration of the incidence of RAS and BRAF circulating cell free DNA and biomarkers including micro-RNA.

### Specimen collection, processing, and storage

Blood will be collected prior to cycle 1, 5, 9, 13 (and every 4 cycles thereafter) of study treatment and at the time of progression. Collection will continue every 3 months (+/-1 month) subsequent to ending treatment for up to 3 additional draws.

The study coordinator should notify the TRLC of possible samples via email to [name] (e.g. [[contact]](mailto:[contact])) or her designee and preferably at least a day in advance of sample collection.

One 4 ml K2EDTA purple top tube will be filled at each timepoint. After collection, tubes will be inverted gently several times, and then kept upright on ice or at 4°C and taken to the Translational Research Laboratory Core (TRLC) in Beckman building, room 4320 as soon as convenient. Tubes are to be labeled with participant initials, study number, MRN, and date and time of collection.

The TRLC will process the samples for plasma storage. Blood samples should be centrifuged (10-20 min at 1100-1300g at RT) within four hours of blood collection. Plasma will be distributed into approximately four 500µl aliquots into cryovials and placed on ice within 1 hour of centrifugation. Aliquots should be stored at < -70°C.

Data points will include the following:

- Date and time of blood collection
- Number and volume of aliquots prepared
- Date and time into  $< -70^{\circ}\text{C}$  and date and time retrieved from freezer
- Any freeze-thaw that occurs with a sample for any reason
- Any variations or deviations from the orientations in this section, problems, or issues, which should also be promptly communicated to the PI.

## 10.0 STUDY CALENDAR

Day 1 of each cycle is defined as the day of agent administration. In the absence of a treatment hold, each cycle lasts 14 days but may be extended up to 5 days or reduced by up to 2 days for participant convenience. Safety evaluations are to be performed within 48 hours of agent administration. If there is a delay in treatment and assessments were already performed, only those assessments deemed necessary by the treating investigator need to be repeated within 48 hours of agent administration. The interval for CT scan is +/- 2 weeks.

**10.1 Table 10.0 Study Activity Calendar**

	Screening a	Day 1 of Cycles 1-4 b				Day 1 of remaining cycles b,d				End of Tx e	30-Day Post Drug f	Follow-Up g
		Cycle 1 c	Cycle 2	Cycle 3	Cycle 4	Cycle 5, 9	Cycle 6, 10	Cycle 7, 11	Cycle 8, 12			
Informed consent h	X											
Background information/history i	X											
Inclusion/Exclusion criteria j	X											
Vital Signs k	X	X	X	X	X	X	X	X	X	X		
ECOG Performance Status l	X										X	
Physical exam	X	X	X	X		X		X		X		
Adverse event assessment m		X	X	X		X		X		X	X	
Concomitant meds review n	X	X	X	X		X		X		X	X	
Hematology o	X	X	X	X	X	X	X	X	X	X		
Serum Chemistry p	X	X	X	X	X	X	X	X	X	X		
Serum Pregnancy Test q	X									X		
Carcinoembryonic Antigen (CEA)	X r	X		X		X		X		X s		
Blood for correlative studies t		X				X				X s		X u
Imaging – PET/CT or MRI v	X w					X				X s		
Response Assessment x						X				X s		
Study Treatment y		X	X	X	X	X	X	X	X			
Progression Assessment												X z
Survival												X aa

- To be performed within 14 days from start of study agents, except imaging and CEA to be performed within 21 and 28 days of start of study agents, respectively (footnotes 'w' and 'r').
- Day 1 is defined as the day of agent administration. Safety evaluations to be performed within 48 hours of agent administration. If there is a delay in treatment and assessments were already performed, only those assessments deemed necessary by the treating investigator need to be repeated within 48 hours of agent administration. In the absence of a treatment hold, each cycle lasts 14 days, but may be extended up to 5 days or reduced by up to 2 days for participant convenience.
- Screening assessments may serve as cycle 1 day 1 assessments if performed within 7 days of day 1, except in the event that there are indications that the participant's condition is deteriorating, for which laboratory evaluations should be repeated within 48 hours prior to initiation of study agent.
- Assessments/activities to continue at four cycle repeats, i.e. use Cycle 5 information for Cycle 9, 13, 17 etc. participants will be taken off study treatment at the time of progression.

- e. End of treatment assessments to be performed after last study drug administration except where noted in footnote 's'. Assessments may continue where indicated for ongoing reportable adverse events or events resulting in a dose modification.
- f. A contact/visit for review of adverse events, ECOG performance status, and concomitant medication review, is to be performed at 30 days +/- 2 days after the last study drug is given. This may be performed via documented phone conversation with a study nurse or clinician. All participants will be followed until resolution or stabilization of any serious or reportable adverse events occurring during treatment or starting within 30 days of last study drug.
- g. Every 3 months (+/-1 month). Participants will be followed for samples for correlative studies (at 3 and 6 months only), progression information (for those who do not progress while on therapy), and survival.
- h. Informed consent process to be fully documented: e.g. prospective participant had sufficient time for deliberation, all questions were answered, treatment options provided by MD, full study reviewed including risks, and a copy of signed consent given to participant.
- i. Background/history – to include a review of treatment history for colorectal cancer, any ongoing medical conditions and medical history pertaining to eligibility on study and involvement during study.
- j. Inclusion/exclusion criteria. Source documentation providing investigator's confirmation that patient has met all eligibility criteria must be available prior to registration.
- k. Vital signs: Weight, heart rate, blood pressure, respiration rate, temp. Height required only at baseline.
- l. See Appendix A for ECOG scale.
- m. Adverse events experienced by participants will be collected and recorded from the pre-treatment C1D1 safety assessments up to 30 days of the last dose of study medication. The period for collection and recording of AEs is extended for participant with ongoing "reportable" adverse events that are related to study agent. Adverse event reporting begins for events that occur after start of study treatment. Toxicities will be assessed using CTCAE v.4.0 except for skin and nail toxicities (see Appendix B).
- n. Concomitant medication and reason for administration should be documented in the case history.
- o. Hematology – erythrocytes (RBC), hemoglobin, hematocrit, platelets, total WBC plus differential (neutrophils, lymphocytes, monocytes, eosinophils, basophils).
- p. Serum chemistry – albumin, alkaline phosphatase, ALT (SGPT), AST (SGOT), bilirubin (total), calcium, carbon dioxide, chloride, creatinine, glucose, **magnesium**, potassium, protein (total), sodium, urea nitrogen.
- q. Serum pregnancy test only for women of child bearing potential.
- r. CEA to be performed within 28 days of start of treatment.
- s. Do not need to be repeated if performed within 21 days before decision to end treatment.
- t. At the time of routine sample collection, one 4 ml purple top (K2EDTA) tube will be collected, gently inverted several times and then maintained in an upright position at 4°C or on ice, and taken to the TRLC in Beckman, room 4320 within ~ 3 hours and as early as convenient. The TRLC should be notified of planned samples via email to [name] or (e.g. [contact]) or her designee preferably at least a day in advance. Tubes are to be labeled with participant initials, study number, MRN, and date and time of collection. (See Section 9.0)
- u. During follow up, blood for correlative studies to be taken 3 times only (e.g. 3, 6, 9 months but not after).
- v. Imaging studies including a CT chest, abdomen, and pelvis. A PET/CT or MRI can be used if deemed clinically necessary. The interval for scans is +/- 2 weeks.
- w. To be performed within 21 days of start of treatment.
- x. Response assessment using RECIST 1.1 criteria (Section 11), at time of imaging and as indicated clinically.
- y. Study treatment of panitumumab, irinotecan, leucovorin, 5-FU detailed in Section 5.2.
- z. Progression assessment for participants who have yet to progress. It will not be a protocol deviation if this assessment is not performed. All visits will be directed by standard of care practices.
- aa. Survival assessment to occur via medical record review, review of social security registry, or phone call.

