#### 11.1.4 Evaluation of Best Overall Response:

The best overall response is the best response recorded from the start of the treatment until disease progression/recurrence (taking as reference for progressive disease the smallest measurements recorded since the treatment started). The participant's best response assignment will depend on the achievement of both measurement and confirmation criteria.

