#### **For Participants with Measurable Disease (*i.e.*, Target Disease)**

Target Lesions	Non-Target Lesions	New Lesions	Overall Response	Best Overall Response when Confirmation is Required*
CR	CR	No	CR	≥4 wks. Confirmation**
CR	Non-CR/Non-PD	No	PR	≥4 wks. Confirmation**
CR	Not evaluated	No	PR	
PR	Non-CR/Non-PD/not evaluated	No	PR	
SD	Non-CR/Non-PD/not evaluated	No	SD	Documented at least once ≥4 wks. from baseline**
PD	Any	Yes or No	PD	no prior SD, PR or CR

Any	PD***	Yes or No	PD
Any	Any	Yes	PD

\* See RECIST 1.1 manuscript for further details on what is evidence of a new lesion.  
\*\* Only for non-randomized trials with response as primary endpoint.  
\*\*\* In exceptional circumstances, unequivocal progression in non-target lesions may be accepted as disease progression.  
Note: Participants with a global deterioration of health status requiring discontinuation of treatment without objective evidence of disease progression at that time should be reported as “*symptomatic deterioration.*” Every effort should be made to document the objective progression even after discontinuation of treatment.

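### A first response seen in the 21 days before treatment stops has no required scan to confirm it, although confirmation is part of a primary endpoint

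*Combined protocol and SAP*

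**What the plan says.** **Endpoint.** The Synopsis (Endpoints) and Section 1.0 make response rate primary, alongside PFS. Section 11.1.4 states: "The participant's best response assignment will depend on the achievement of both measurement and confirmation criteria". The table for measurable disease gives the requirement as "≥4 wks. Confirmation", with the note "Only for non-randomized trials with response as primary endpoint". This trial has a single arm and response rate is a primary endpoint, so the requirement applies. Section 11.1.4 also sets the period: "The best overall response is the best response recorded from the start of the treatment until disease progression/recurrence".

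**Calendar.** Section 2.2 and Table 10.0 schedule imaging and response assessment every four cycles (8 weeks), with a window of 2 weeks either way, and once more at end of treatment. Both end-of-treatment entries carry footnote s: "Do not need to be repeated if performed within 21 days before decision to end treatment". Footnote e asks for these assessments after the last dose but sets no date.

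**After treatment.** The Follow-Up column has no entry for imaging or response assessment. It has a progression assessment every 3 months (1 month either way), of which footnote z says: "It will not be a protocol deviation if this assessment is not performed". Footnote x allows response assessment when there is a clinical indication.

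**Gate.** Under Section 13.1, stage 2 opens if stage 1 (14 participants) yields one response, or if four or more participants are free of progression at 4 months. It does not say whether the response must be confirmed.

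**The concern.** The endpoint definition needs a second look at least 4 weeks after the first response. The calendar removes the end-of-treatment look exactly when the last scan is recent, and does not ask whether that scan was the first to show response. Nothing mandatory replaces it.

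The participants exposed are those who respond and then stop early for a reason other than progression, such as toxicity or their own request. Section 13.1 keeps all eligible treated participants in the main response analysis, so such a participant stays in the denominator. Whether he or she reaches the numerator then depends on a scan that somebody chose to order. For a primary endpoint, that leaves room for inconsistent handling by people who already know the first result.

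**Working it through.** **1. Day counts.** Inputs: waiver 21 days (footnote s); confirmation 4 weeks = 28 days (Section 11.1.4 table); scan interval 8 weeks = 56 days (Section 2.2). The confirmation entry is read as covering PR as well as CR, since the text of 11.1.4 draws no distinction. Let *t* be the days from the first response scan to the decision to stop, with no progression and no scan in between.

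| *t* (days) | End-of-treatment scan | Can a required scan confirm? |
|---|---|---|
| 0–21 | waived | no; none is required |
| 22–27 | required, date not fixed | only if taken on day 28 or later |
| 28 or more | required | yes |

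A participant with response on two consecutive scheduled scans is already confirmed at the nominal spacing of 56 days. If the two windows are used in opposite directions the spacing is 56 − 14 − 14 = 28 days, still enough.

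**2. Can a stop fall in the first row under the protocol's own rules?** Yes. Suppose the cycle 5 day 1 scan shows a first PR and that dose is held for toxicity. The last administration was cycle 4 day 1, nominally 14 days earlier. Section 6.2.1 item 9 requires discontinuation, unless an exception is agreed, when resumption criteria are not met within 28 days of the last treatment. That limit falls 28 − 14 = 14 days after the scan, inside the waiver. Table 6.2.2 also mandates permanent discontinuation for confirmed interstitial lung disease and for grade 4 panitumumab-related skin, nail or other unspecified non-hematologic toxicity. Section 5.4 allows removal at the participant's request.

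**3. Effect on the response rate.** One response not credited: 1/25 = 4 points at the final analysis; 1/14 = 7.1 points in stage 1.

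**4. Effect on the gate.** The plan's own figures reproduce:
- No response in 14 at a true rate of 20%: 0.80^14 = 4.4% (stated 4.4%).
- Fewer than 4 of 14 progression-free: 95.6% at a 4-month rate of 10% (stated above 95%) and 2.87% at 50% (stated below 3%).
- Early stopping at 5% response and 10% PFS: 0.95^14 × 0.956 = 0.488 × 0.956 = 46.6% (stated 46%), treating the two outcomes as independent.

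Now make two assumptions that the documents do not state: a share *f* of true responders goes unconfirmed, and the gate counts confirmed responses only. At a true rate of 20%, P(none confirmed in 14) = (1 − 0.20(1 − *f*))^14:

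| *f* | P(none confirmed in 14) |
|---|---|
| 0 | 4.4% |
| 0.10 | 6.2% |
| 0.20 | 8.7% |
| 0.30 | 12.1% |

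Stopping also needs fewer than 4 progression-free. At *f* = 0.20, again under independence:

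| 4-month PFS | P(fewer than 4 of 14) | P(stop) | P(stop) at *f* = 0 |
|---|---|---|---|
| 10% | 95.6% | 8.3% | 4.2% |
| 30% | 35.5% | 3.1% | 1.6% |
| 50% | 2.87% | 0.25% | 0.13% |

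Response and freedom from progression are likely to be positively associated, which would raise the stopping figures. They cannot exceed the smaller of the two component probabilities: at *f* = 0.20, 8.7%, 8.7% and 2.87% in the three rows.

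**The case against.** **A reader might infer that such a response can never be confirmed or counted.** The documents do not support that. Footnote s excuses a repeat scan without forbidding one, footnote x allows clinically indicated assessment, and best response runs to progression and not to the end of treatment. A voluntary, clinically indicated or follow-up scan before progression can therefore confirm. The gate wording does not mention confirmation, so it is also not established that an unconfirmed response would be left out there.

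**A reader might blame the waiver for being shorter than the confirmation interval.** That reverses the effect. A shorter waiver makes more end-of-treatment scans mandatory, and a 28-day waiver would excuse more of them. What is missing is a required confirming scan for this group.

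**The route may be rare.** If the response scan was done on or before the last dose, a stop at the 28-day limit of Section 6.2.1 item 9 comes 28 days or more after the scan and is covered. For severe infusion reactions, discontinuation is left to the investigator. The documents give no distribution of stopping times, so no share of responders lost can be derived.

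**Not crediting an unconfirmed response is conservative by design.** This stands in part. A single PR is not an established response under the protocol's definition, so it cannot be said that true responses are being discarded. But here the confirming look is absent because the calendar does not ask for it, not because the response failed to last.

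**Conclusion.** The point holds in a narrow form. The calendar does not deliver the measurement that the primary endpoint's definition needs when a first CR or PR is seen 0 to 21 days before a stop without progression, and it may not deliver it at 22 to 27 days. Participants with a response on two scans at least 4 weeks apart, and those who stop 28 days or more after the first response scan, are not affected.

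Few participants are likely to be involved, though the number cannot be estimated from the documents. Each one classed as unconfirmed costs 4 points of response rate in 25. The effect on the stage 1 decision is modest because of the PFS arm, and it arises only if response in Section 13.1 means confirmed response. No design probability in the plan is wrong on this account. This is a cheap improvement and not a flaw in the design.

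**What to change.** Amend footnote s of Table 10.0 along these lines: the 21-day waiver of imaging and response assessment does not apply when the participant's last assessment was a first, unconfirmed CR or PR; for that participant, the end-of-treatment scan is taken at least 4 weeks after the scan that first showed response. This closes both the 0–21 day and the 22–27 day gaps, and uses a scan already in the calendar.

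**Cost:** one sentence in the calendar. In a few participants a scan that would have been waived is taken, or the end-of-treatment scan comes later than it otherwise would.

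Whether the gate in Section 13.1 counts confirmed or unconfirmed responses is a separate matter of missing detail. It could be stated in the same amendment, but the change to footnote s does not depend on it.
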